## V. DESIGN

This is a randomized, placebo-controlled, cross-over, single-center trial. Study drug is Botulinum toxin type A (BOTOX®). Subjects who meet the inclusion criteria for the study will be randomized to either the treatment or placebo arm.

**ARM 1 - Treatment:** Injection solution will consist of 100 units of BOTOX® in 10 cc of preservative free normal saline, or

**ARM 2 - Placebo:** Injection solution will consist of 10 cc preservative free normal saline.

The Week 16 Visit will be the end of the study participation for those subjects in Arm 1 and who did not develop ED (as defined as a drop in IIEF scores of more than 4 points from Baseline IIEF score). The Week 16 Visit will be the end of study participation for subjects in Arm 2 and who developed ED. For subjects in Arm 2, crossover to BOTOX treatment will begin after the Week 16 Visit by repeating the study schedule as for Week 0 to Week 16. Continuation visits at Months 6, 9, and 12 will occur for subjects in Arm 1 and who developed ED.

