## VII. SCHEDULE OF EVENTS

PROCEDURE	Baseline (Pre-treatment)	Week 0 Clinic Visit	Week 2 Phone Visit	Week 4 Clinic Visit	Week 6 Phone Visit	Week 8 Clinic Visit	Week 10 Phone Visit	Week 12 Clinic Visit	Week 14 Phone Visit	 Week 16 Clinic Visit (  End of Study) (  Placebo Crossover)	 Month 6 Clinic Visit	 Month 9 Clinic Visit	 Month 12 Clinic Visit (End of Study)
Signed, written informed consent	X												
Medical history	X												
Physical examination	X									X	X	X	X
Blood pressure, pulse, O 2 saturation	X									X			
Penile injection: Caverject 20mcg/cc	X									X			
Penile curvature assessment & photos	X									X			
Penile ultrasound	X									X			
IIEF questionnaire	X									X			
Randomization	X												
Penile injection: BTX-A or  Placebo		X		X		X		X					
Collect AE information		X	X	X	X	X	X	X	X	X	X	X	X
Concomitant meds	X	X		X		X		X		X	X	X	X

End of study for subjects receiving BOTOX and did not develop ED (as defined as a drop in IIEF scores of more than 4 points from Baseline IIEF score).

End of study participation for subjects receiving placebo and develop ED.

For subjects receiving placebo, crossover to BOTOX treatment will begin by repeating the study schedule as for Week 0 to Week 16.

Continuation visits for subjects receiving BOTOX and developed ED.

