Subjects randomized to ARM 2 will receive one injection of 10cc preservative normal saline at Weeks 0, 4, 8 and 12.

All subjects will be telephoned two weeks after each injection to inquire on the occurrence of any adverse events. Subjects will be asked a general, non-direct question such as, "How have you been feeling since the last visit?" Direct questioning will then be done as appropriate.

At the completion of 16 weeks (4 weeks after last treatment), subjects will have a repeat penile injection of Caverject, penile pictures will be taken, and penile ultrasonography will be performed. Subjects will also be asked to complete the IIEF again.

The Week 16 Visit will be the end of the study participation for those subjects in Arm 1 and who did not develop ED (as defined as a drop in IIEF scores of more than 4 points from Baseline IIEF score). Subjects developing ED, will have continuation visits at Months 6, 9, and 12. At these visits, a complete physical will be done. Information about any adverse events and changes in concomitant medications will be collected. The subjects will complete the IIEF questionnaire.

If at the end of 16 weeks there is a significant improvement in the subjects treated with BTX-A as compared to the placebo arm, the men in the placebo arm will be given the option to cross over into the treatment arm and complete a 12 week course of BTX-A injections (1 saline injection, 1 Botox injection, 2 saline injections). For those in Arm 2 who develop ED, participation will end after the Week 16 visit.

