**D. Safety Monitoring:**

During the treatment phase of the study, participants will be asked about AEs at each visit. The investigators and/or the study coordinator will document all AEs. All AEs occurring during the course of the study will be collected, documented, and reported to the PI. AEs will be followed to the point of a satisfactory resolution. Study participants may have their study drug discontinued or they may be withdrawn from the study if the PI determines it is the best decision in order to protect the safety of the participant. Additional AE information is contained in Appendix II - Adverse Event Reporting.

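### Arm 2 men who develop ED leave at Week 16 with no stated follow-up, and the schedule omits the IIEF from the continuation visits that follow ED after BTX-A

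*Combined protocol and SAP*

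**What the plan says.** ED is defined in Section V as a fall of more than 4 IIEF points from baseline. What happens next depends on treatment.

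- **Arm 2, exit.** Section V: "The Week 16 Visit will be the end of study participation for subjects in Arm 2 and who developed ED". Section VII, footnote 2: "End of study participation for subjects receiving placebo and develop ED". Section VIII, closing sentence: "For those in Arm 2 who develop ED, participation will end after the Week 16 visit".
- **BTX-A, continued follow-up.** Section V: "Continuation visits at Months 6, 9, and 12 will occur for subjects in Arm 1 and who developed ED". Section VII, footnote 4: "Continuation visits for subjects receiving BOTOX and developed ED".
- **Content of the continuation visits.** Section VIII lists a physical examination, adverse events and concomitant medication, and adds: "The subjects will complete the IIEF questionnaire". The Section VII table marks the IIEF at Baseline and Week 16 only.
- **Safety rule.** Section XIII.D, for all participants: "AEs will be followed to the point of a satisfactory resolution".
- **Risk.** Section IX says that the risk of ED after the study injections is not known.

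**The concern.** The injection procedure is the same in both arms apart from the solution: sessions at Weeks 0, 4, 8 and 12, each with a lidocaine block and about 20 to 30 needle passes into the plaque. ED could therefore arise in either arm. A man in Arm 2 who meets the definition leaves at the visit where it is found, while a man given BTX-A with the same finding is seen for the rest of the year.

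Two things are at stake. A possible harm of the procedure would go unfollowed in the control arm, although the safety section sets a general follow-up rule. And if ED in Arm 1 persists or resolves, there is no control observation to set beside it. Separately, if staff work from the schedule table, the instrument that defines ED would not be given at the visits that exist because of ED.

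**Working it through.** The plan gives no figure on this point to reproduce. It states no expected ED rate and no SD for IIEF change, and the 10 per arm in Section XI comes without inputs. The check is mainly a comparison of sections.

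**1. Scheduled visits after Week 16 for a man with ED**

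| Man with ED | Section V | Section VII | Section VIII | Visits |
|---|---|---|---|---|
| Arm 1 | Months 6, 9, 12 | Months 6, 9, 12 (footnote 4) | Months 6, 9, 12 | 3 |
| Arm 2, not crossed over | ends at Week 16 | ends at Week 16 (footnote 2) | ends at Week 16 | 0 |
| Arm 2, ED after crossover | visits tied to Arm 1; only Weeks 0 to 16 are repeated | visits tied to receiving BOTOX | joins the treatment arm; continuation not stated | unclear |

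The Arm 2 exit rule appears in three places and is consistent. It is not a slip in one sentence.

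**2. Against Section XIII.D.** The follow-up rule there has no limit by arm. The documents never expressly call the IIEF fall an adverse event. It is, however, a worsening after a study injection, and ED is named as a risk in Section IX, so a plain reading brings it under the rule. No section says how follow-up would continue after an Arm 2 man's participation ends. The fixed Month 12 end for Arm 1 is not tied to resolution either.

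**3. Unexposed men with ED observed after Week 16.** Arm 2 men with ED exit. The other Arm 2 men either cross over or have no later follow-up described. Those who cross over have BTX-A at the second of their four sessions and their next IIEF at the end of the repeated course, so any ED found then follows exposure. The planned number of unexposed men with ED seen after Week 16 is 0.

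**4. IIEF at Months 6, 9 and 12.** Required in Section VIII; unmarked in all three columns of the Section VII table.

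**5. Timing after crossover.** The repeated course ends 16 + 16 = 32 weeks after the original Week 0. Month 6 is 6 × 52/12 = 26 weeks. Counted from the original start, the Month 6 visit would already have passed when ED is detected. No section says which start date applies.

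**6. What equal follow-up could offer.** Assume an ED rate p of 10%, 20% or 30% in each arm of 10; the documents give none.

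- Expected men with ED per arm = 10p: 1, 2, 3.
- Chance of at least one in both arms = [1 − (1 − p)^10]²: 42%, 80%, 94%.
- Smallest two-sided Fisher p-value with k men with ED per arm, all recovering in one arm and none in the other = 2/C(2k, k): 2/20 = 0.10 for k = 3, and 2/70 = 0.029 for k = 4.
- Chance of at least 4 in both arms: 0.02%, 1.5%, 12%.
- Power of Fisher's test at an assumed two-sided 5% level for recovery of 20% versus 80%: 0.05%, 1.8%, 9.3%.

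Equal follow-up would often give a control observation, but not a test.

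**The case against.** **What the other side can fairly say.** ED recovery is not among the outcomes in Section XII. The IIEF is compared between arms at baseline and Week 16, and that randomised comparison is intact. Men with ED are a subgroup formed after randomisation, and step 6 shows that equal follow-up would not attribute persistent ED to BTX-A. Section XIII.D does not confine follow-up of adverse events to study visits, so ending participation and following an event could coexist. All of this stands. It limits the point to safety description and to a missing mechanism; it does not supply the mechanism or the unmarked IIEF.

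On crossover, Section VIII speaks of joining the treatment arm, and with footnote 4 that suggests crossed-over men with ED are covered. That is a reasonable reading, but Section V does not say so and the start date remains open.

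**Stronger readings a reader might infer.**

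- *Section VIII contradicts itself on Arm 2*, because "Subjects developing ED, will have continuation visits at Months 6, 9, and 12" names no arm. In context it follows a sentence about Arm 1, and the section's closing sentence excludes Arm 2. There is no conflict on this.
- *Staying or leaving at Week 16 reveals the arm.* The documents state no blinding, and Section VI assigns arms by odd and even enrolment number. Nothing further is lost.
- *A count of Arm 2 men released with unresolved ED.* One could assume an SD for IIEF change and calculate how often noise alone crosses the threshold. The documents give no SD, and men flagged by noise have no true change to resolve. Such a figure does not measure lost cases.

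**Conclusion.** The point holds as a gap in safety follow-up and an inconsistency between sections. For a man with ED, scheduled visits after Week 16 are 3 in Arm 1 and 0 in Arm 2, and the number of unexposed men with ED under observation is 0. Section XIII.D and the exit rule need reconciling, since no route for following an Arm 2 man's ED is described; this rests on reading an IIEF-defined ED as an adverse event. The omission of the IIEF from the schedule needs no assumption: as the table stands, ED recovery may go unmeasured even in Arm 1.

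The primary outcome is not touched. The loss is of descriptive control information on a possible harm, and its size depends on an ED rate that the documents do not give. The amendment is worth making because it is cheap.

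**What to change.** 1. Mark the IIEF in the Month 6, 9 and 12 columns of the Section VII table, to match Section VIII.
2. Reconcile Section V, Section VII (footnotes 2 and 4) and Section VIII with Section XIII.D, so that collection of adverse-event and IIEF data on ED does not depend on arm, and state how those data are obtained once treatment visits have ended.
3. State whether crossed-over men who develop ED have the continuation visits, and from which date their months are counted.
4. Describe any resulting data on the course of ED as descriptive.

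These changes concern data collection and consistency only. Treatment of ED and eligibility for crossover are left to the sponsor. If Arm 2 men with ED were later given BTX-A, they would cease to be unexposed controls from that time. The cost is a short amendment and a few further contacts for any Arm 2 men with ED.

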## VI. RANDOMIZATION PROCEDURES:

The subjects will be randomized to the arms as they are enrolled and meet eligibility criteria. The odd number (1, 3, 5...) of subjects will be in ARM 1 and even numbers (2, 4, 6...) of subjects will be in the ARM 2. The randomization scheme will not result in selection bias.

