## VIII. PROCEDURES

Subjects who meet the inclusion criteria for the study will be randomized to either the treatment or placebo arm. Prior to treatment, all subjects will have a penile injection with Caverject 20mcg/cc to induce a penile erection. During the erect state, penile curvature will be assessed, pictures will be taken for later measurement of penile curvature, and ultrasound will be used to assess penile blood flow and plaque size. A penile duplex with intercavernosal injections of a vasoactive substance is part of our standard care for Peyronies disease diagnosis. Subjects will also be asked to complete the International Index of Erectile Function (IIEF) questionnaire.

Injections will be performed using our standard protocol currently used for verapamil injections, but instead we will be using 100 units of BTX-A in 10cc of preservative free normal saline, or 10cc of preservative free normal saline for placebo and plaque breakdown injections. The standard injection procedure consists of the following:

1. Subjects will be explained the risks and benefits of the procedure and will give informed consent.
2. Blood pressure, pulse, and oxygen saturation will be monitored throughout the procedure.
3. A penile block with 10cc of lidocaine without epinephrine will be given, followed by an observation period of 10 minutes to assure no immediate adverse reaction to lidocaine.
4. Approximately 20 to 30 injections with a 20 gage needle will be given directly into the penile plaque. The skin will not be punctured with each injection, but the needle will move within the plaque. Injection solution will consist of 100 units of BTX-A in 10 cc of preservative free normal saline, or 10 cc of preservative free normal saline.
5. Subjects in the placebo arm will only receive 10 cc of preservative free normal saline.
6. Subjects will be monitored for 1 hour after the procedure to ensure that their vital signs are stable and that there are no signs of penile hematoma.
7. Safety will be assessed by following the subject closely for one hour after the procedure.
8. Subjects will be given strict instructions to call and return to the clinic or the ER for any adverse side effects.

Subjects randomized to ARM 1 will receive one injection of 10 cc preservative normal saline at study start (week 0), followed by 100 U Botox in 10cc saline at visit two (week 4), then saline injections at weeks 8 and 12, thus a total of 4 injections (1 saline, 1 Botox, 2 saline).

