## **XI. SAMPLE SIZE**

This will be a pilot study and therefore 10 subjects in each arm, for a total of 20 subjects, will allow us to determine if the therapy is effective. To allow for screen failures, 45 subjects are planned for screening.

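### Men are allocated at Baseline, but under Section VIII the arms first differ at Week 4, so a man lost in Weeks 0–4 is lost after allocation and before he could have received BTX-A

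*Combined protocol and SAP*

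**What the plan says.** **When men are allocated.** Section VI: "The subjects will be randomized to the arms as they are enrolled and meet eligibility criteria". The Section VII schedule marks randomization in the pre-treatment Baseline column and nowhere else. The rule is alternation: "The odd number (1, 3, 5...) of subjects will be in ARM 1", with even numbers going to Arm 2. Section XVIII gives subjects consecutive numbers.

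**What each arm receives.** Section VIII is the only place that states injection content session by session. The active arm opens with a session that contains no toxin: "Subjects randomized to ARM 1 will receive one injection of 10 cc preservative normal saline at study start (week 0"). Its single BTX-A session comes second, and the two that remain are again without toxin: "followed by 100 U Botox in 10cc saline at visit two (week 4), then saline injections at weeks 8 and 12". For the control arm: "Subjects randomized to ARM 2 will receive one injection of 10cc preservative normal saline at Weeks 0, 4, 8 and 12". The cross-over text in the same section repeats the active sequence: "complete a 12 week course of BTX-A injections (1 saline injection, 1 Botox injection, 2 saline injections").

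**Less specific text.** Sections III and V describe the Arm 1 solution as BTX-A without naming a session. The schedule row in Section VII shows BTX-A or placebo at Weeks 0, 4, 8 and 12.

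**Losses and numbers.** Section X lets a man withdraw at any time and leaves other withdrawals to the investigator's discretion. Section XI plans "10 subjects in each arm, for a total of 20 subjects", and its only allowance is this: "To allow for screen failures, 45 subjects are planned for screening". Section XII names a t-test on change in curvature from Baseline to Week 16. It defines no analysis set and no rule for a missing Week 16 photograph.

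**The concern.** On the Section VIII sequence, the first four weeks are in effect a saline run-in common to both arms, but men enter it already allocated. Week 0 is a demanding session: a penile block, then 20 to 30 needle passes into the plaque. Some men may not continue. A loss at this stage cannot be an effect of BTX-A, yet it can take an observation from an arm of 10.

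Two things are at stake. The first is precision, because nothing in Section XI covers losses after allocation. The second is comparability. Staff can read the arm from the enrolment number, and Section V describes a placebo-controlled design without stating masking. Knowledge of the arm could therefore influence who leaves, or who is withdrawn, while the two arms are still being treated identically.

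Eligibility adds to this. Exclusion 10, on aspirin, NSAIDs and Coumadin, is timed to the days before the Botox injection. In Arm 1 that injection falls at Week 4, so this criterion cannot be fully confirmed at Baseline, and late exclusions under it could fall unequally on the arms.

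**Working it through.** **1. Where the arms diverge (Section VIII)**

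| Session | Arm 1 | Arm 2 |
|---|---|---|
| Week 0 | saline | saline |
| Week 4 | BTX-A | saline |
| Week 8 | saline | saline |
| Week 12 | saline | saline |

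Allocation (Baseline) comes before a whole session that is the same in both arms.

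**2. The plan's own figure.** The total of 20 is 10 + 10. No alpha, power, effect size or standard deviation is given, so 10 per arm cannot be reproduced. Working backwards with an assumed two-sided alpha of 0.05 and 80% power (noncentral t), 10 per arm detects a standardised difference d = 1.325. This is a yardstick, not a planned value.

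**3. Precision.** Assumption: 1 to 3 of the 20 men (5% to 15%) are lost in Weeks 0–4 and have no Week 16 photograph. With a common standard deviation, the standard error relative to plan is

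ratio = √[(1/n₁ + 1/n₂) / (1/10 + 1/10)]

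- One lost, 9 v 10: √(0.2111/0.2) = 1.027, a rise of 2.7%.
- Two lost, 9 v 9: √(0.2222/0.2) = 1.054, a rise of 5.4%.
- Three lost, 8 v 9: √(0.2361/0.2) = 1.087, a rise of 8.7%.

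**4. Power, on the yardstick.** At d = 1.325, power falls from 80% to 77.6% (9 v 10) and 75.1% (9 v 9). Four losses (8 v 8), beyond the assumed range, would give 69.3%. At d = 1.0, power is 56.2% with 10 per arm and 51.3% with 9.

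**5. Chance of at least one early loss among 20.** 1 − (1 − rate)²⁰ gives 64% at a 5% rate, 88% at 10% and 96% at 15%. The rates are assumptions.

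**6. What Week 4 allocation needs.** To have 20 men at Week 4, 20/(1 − rate) must start Week 0: 21.1, 22.2 or 23.5 at 5%, 10% or 15%, which round up to 22, 23 or 24.

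**7. Whether moving the allocation is enough.** If odd/even enrolment numbers are kept, the arm is known from Baseline whatever the schedule cell says. If men are renumbered at Week 4 but still alternate, staff can foresee the next arm. So the timing change limits arm-driven loss only together with a concealed random list.

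**The case against.** The strongest reply is that allocating before a multi-session course is ordinary practice. Section VIII defines the active regimen as four sessions and calls the same four a BTX-A course at cross-over. It also speaks of saline as a plaque-breakdown injection, so Week 0 can be read as part of the strategy under test. That is fair: Baseline allocation is a design choice, not an error. The plan, however, gives no reason for allocating a full session before the arms differ, and it has none of the safeguards (dropout allowance, analysis set, missing-data rule) that would make early allocation harmless.

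It is also fair that the loss rate is assumed, that the effect on precision is modest, and that Section XI states no power that could be damaged.

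Some stronger readings are tempting but unsupported:

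- *No man in the trial has had BTX-A when these losses occur.* Enrolment is staggered, so earlier men may already be past Week 4. The statement is true only of the man who leaves.
- *Every early leaver costs an observation.* He could still return for the Week 16 photograph, and Section XII does not say he would be dropped.
- *Starting an excluded oral drug forces withdrawal.* Exclusion 3 is an entry criterion, and Section X leaves such withdrawals to discretion.
- *Losses will differ by arm.* No available passage says men are told their arm, and the consent pages were not available. The cross-over option gives placebo men some reason to stay. Differential loss is possible, not shown.
- *The 45 screened men supply replacements.* Section XI sets them aside for screen failures and shows no surplus.

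**Conclusion.** The point holds as a design weakness that is worth correcting. If the Section VIII sequence stands, allocation comes one identical session too early. Any man lost in Weeks 0–4 is then lost after allocation without having been able to receive BTX-A.

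The cost in precision is a 2.7% to 8.7% larger standard error. This rests on the assumption that 1 to 3 of 20 men are lost and have no Week 16 photograph. The possible bias is the more serious matter but cannot be quantified. It depends on the arm being readable from the enrolment number and on masking being absent in practice as well as unstated.

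A reader might infer that moving the randomization cell to Week 4 cures both problems. It does not. With alternation retained the arm stays foreseeable, and the gain in precision comes only if a few extra men start Week 0. Losses from Week 4 to Week 16 are untouched.

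**What to change.** 1. Reconcile Sections III and V and the injection row of the Section VII schedule with the session contents in Section VIII, so that one sequence is stated throughout. The steps below apply if the Section VIII sequence stands.
2. In Section VII, move randomization from Baseline to the Week 4 visit, after concomitant medications and eligibility are rechecked and immediately before that day's injection. Describe Week 0 in Sections V, VI and VIII as a session common to all men.
3. In Section VI, replace odd/even assignment with a concealed random list, so that the arm cannot be foreseen during Weeks 0–4.
4. In Section XI, count the 10 per arm from men allocated at Week 4.

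**Cost.** Changes of wording, one moved schedule cell, and the preparation of a random list. Concomitant medications are already collected at Week 4, and no visit, dose or Baseline measurement changes. Results would apply to men who complete one saline session. About 1 to 3 men under the assumed losses (22 to 24 starting in all, once losses among replacements are allowed for and rounded up) may undergo Week 0 without being allocated.

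If the sponsor prefers to keep Baseline allocation, the plan should still use a concealed list, keep all allocated men in the primary analysis, state a missing-data rule and add a dropout allowance. The analysis rule and allowance for losses after Week 4 are needed in either case.
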